## 5.2. Determination of Sample Size

The study plan is to enroll approximately 450 patients in total, with 300 HR+, HER2- locoregionally recurrent or metastatic breast cancer patients who have not received prior endocrine therapy in Cohort A and 150 HR+, HER2- locoregionally recurrent or metastatic breast cancer patients in Cohort B. Assuming approximately 10% screening failure, the study will enter approximately 500 patients.

The approximate 300 patients qualified for Cohort A will be randomized in a 2:1 ratio to Arm A1 (abemaciclib plus NSAI; 200 patients) and Arm A2 (placebo plus NSAI; 100 patients). Patients will be randomized using the following stratification factors: nature of disease (visceral metastases vs. non-visceral metastases) and prior (neo)adjuvant endocrine therapy (prior therapy

with disease-free interval > 12 months from completion of treatment vs. prior therapy with disease-free interval ≤ 12 months from completion of treatment vs. no prior therapy).

A 2-look group-sequential design of the primary endpoint will be used to accommodate an event driven plan for the interim and primary PFS analyses (see protocol Section 12.2.6 for details). The primary PFS analysis will be performed after approximately 170 PFS events in Cohort A have occurred (ie, approximately 43% censoring rate). Assuming a hazard ratio of 0.626, this sample size yields at least 81.4% statistical power to detect superiority of the abemaciclib plus NSAI arm over the placebo plus NSAI arm with the use of a 1-sided log-rank test and a type I error of 0.025. If the true median PFS for the placebo plus NSAI arm is 14.4 months, then the hazard ratio of 0.626 amounts to an approximately 8.6-month (59.7%) improvement in median PFS for the abemaciclib plus NSAI arm under an additional assumption of exponential survival distribution.

Approximately 150 patients will be randomized in a 2:1 ratio to Arm B1 (abemaciclib plus fulvestrant; 100 patients) and Arm B2 (placebo plus fulvestrant; 50 patients). Patients will be randomized using the following stratification factors: nature of disease (visceral metastases vs. non-visceral metastases) and sensitivity to endocrine therapy (primary resistance vs. secondary resistance).

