The design of Cohort B is to ensure 100 patients' exposure of abemaciclib plus fulvestrant and to show 50% of the global study JPBL trial effect size with roughly 80% probability (ie, 80% of chance to observe a hazard ratio less than 0.824, assuming a true hazard ratio of 0.703 by study assumption).

Here, the effect size of the drug is defined as:

$$\delta = \frac{1}{HR} - 1 = \frac{1 - HR}{HR} = \frac{MST_{Test} - MST_{Control}}{MST_{Control}}$$

$MST_{Test}$  and  $MST_{Control}$  are median survival time in test drug group and control drug group, respectively; effect size can be regarded as the percent change of median survival time.

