## 6.7.2. Secondary Efficacy Analyses

### 6.7.2.1. Progression Free Survival of Cohort B

Progression-free survival in Cohort B is the key secondary endpoint for this study. The measurement, rules of censoring of PFS in cohort B are the same as those of PFS in Cohort A (refer to section 6.7.1). Only if statistical significance is declared at the Cohort A interim analysis, the interim analysis of Cohort B will be conducted based on the same data cutoff. If patients in Cohort A continue being followed for PFS until final analysis, the final analysis of Cohort B will be conducted at the same time of Cohort A final analysis. If Cohort A stops early at interim due to efficacy, the final analysis of Cohort B may be conducted after approximately 105 PFS events have been observed in Cohort B (that is, an approximately 30% censoring rate).

Similar to the analysis of PFS of cohort A, the KM method will be used to estimate the PFS curve for each treatment arm. A Cox proportional hazard model stratified by nature of disease and prior (neo)adjuvant endocrine therapy with treatment as a factor will be used to estimate the HR between the two treatment arms and the corresponding CI.

There will be no alpha spent for any test on this endpoint. Statistical tests, such as stratified log rank test and Wald test, will be purely descriptive.

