### 6.7.2.2. Overall Survival

**Overall Survival (OS):** OS duration is measured from the date of randomization of any study drug to the date of death from any cause. For each patient who is not known to have died as of the data-inclusion cutoff date for a particular analysis, OS will be censored for that analysis at the date of last contact prior to the data inclusion cutoff date (contacts considered in the determination of last contact date include AE date, lesion assessment date, visit date, and last known alive date).

The final analysis of OS will be conducted together with the analysis of PFS at study completion. Overall survival, 1-year survival rate and 2-year survival rate by treatment will be analyzed for each cohort.

Kaplan-Meier method and the stratified Cox proportional hazard model will be applied.

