## 6.13. Interim Analyses and Data Monitoring

An interim analysis will be conducted under the auspices of a DMC according to the specifications set forth in the protocol.

An interim analysis on Cohort A will be conducted by the DMC after approximately 119 PFS events have been observed. The interim analysis will be conducted to provide early efficacy information and could potentially result in early communication with regulatory agencies. The O'Brien Fleming alpha spending function (Lan and DeMets 1983) will be used to preserve the

overall type I error. If the analysis of PFS is significant using the p-value boundary described in Section 6.7.1.2, the DMC will be instructed to engage the SMD, who may subsequently convene an IRC to propose actions based upon the DMC's recommendation. All patients will continue follow-up for PFS until study completion, and will remain blinded for the duration of the study unless emergency unblinding (Protocol Section 9.5.2) are met. If Cohort A show early efficacy at interim, the sponsor may consider early stop, unblinding and crossover for this cohort; however, regulatory agencies will be consulted before any action is taken.

The unblinded analysis, including review of the efficacy along with the safety data, will be conducted by the DMC. Only the DMC is authorized to evaluate unblinded interim efficacy and safety analyses. Study sites will receive information about interim results ONLY if they need to know for the safety of their patients.

At the time of the interim analysis, analyses of PFS provided to the DMC will include:

- the boundary values for significance based on the exact number of observed events,
- the p-value for a stratified log rank test comparing the two treatment arms, stratified by the randomization factors,
- an estimate of the HR between the two arms based on a Cox proportional hazards model, stratified by the randomization factors, and
- a KM analysis by treatment arm.

Safety evaluation will be based, at least, on the following data reports:

- summary of patient discontinuations and reasons for discontinuation
- summary of SAEs
- Lilly Safety System reports for all patients with SAEs
- summary of TEAEs

Details pertaining to the conduct of these analyses are provided in the JPBQ DMC Charter.

If statistical significance is not declared at the interim, a final analysis of Cohort A will be conducted with about 170 PFS events.

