The interim analysis of Cohort B is triggered only if statistical significance is declared at the Cohort A interim analysis. No DMC is required for the analysis of Cohort B. The analysis will provide both safety and efficacy information of Cohort B and could potentially result in early communication with regulatory agencies, including consultation of potential decisions regarding early stop, unblinding and crossover before any action is taken.

In the case of early stop and crossover for Cohort A or Cohort B after the interim analysis, Lilly will notify investigators when the crossover begins.

If patients in Cohort A continue being followed for PFS until final analysis, the final analysis of Cohort B will be conducted at the same time of Cohort A final analysis. If Cohort A stops early at interim due to efficacy, the final analysis of Cohort B may be conducted after approximately 105 PFS events have been observed in Cohort B.

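### If Cohort B placebo patients cross over before that cohort's final PFS cut-off, the written PFS rules count their later time and events as placebo and bias the descriptive hazard ratio toward 1

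*SAP*

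**What the plan says.** Crossover is an option in both cohorts. SAP 6.13 and protocol 12.2.14 introduce it with the words "In the case of early stop and crossover for Cohort A or Cohort B after the interim analysis" and have the sponsor tell investigators when it begins. Footnotes b and d to protocol Table JPBQ.9.1 put patients who move from A2 to A1, or from B2 to B1, on the schedule of the abemaciclib arm. For both cohorts crossover is only a possible decision, to be taken after consulting regulators.

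PFS data collection does not end at that point. SAP 6.13 states: "All patients will continue follow-up for PFS until study completion". Where Cohort A stops early, "the final analysis of Cohort B may be conducted after approximately 105 PFS events have been observed in Cohort B" (SAP 6.7.2.1).

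The censoring rules are the seven in SAP Table JPBQ.6.1, repeated in protocol Table JPBQ.12.1. For Cohort B, "The measurement, rules of censoring of PFS in cohort B are the same as those of PFS in Cohort A". None of the seven concerns crossover, unblinding or a change of treatment. SAP 6.1.1 groups patients by randomised arm.

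On inference, SAP 6.7.2.1 says of Cohort B PFS: "There will be no alpha spent for any test on this endpoint", and calls its tests descriptive. SAP 6.7.3 has a Sensitivity Analysis 1 that censors PFS when another anticancer therapy starts before objective progression. It does not say whether crossover counts.

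**The concern.** Under protocol 7.3.2 study drug stops at RECIST progression. A placebo patient still on study drug when crossover opens would therefore generally be progression-free. This is an inference, because the documents do not state who may cross over. Once she takes abemaciclib, Rule 5 or Rule 6 still turns her later progression or death into an event, and the as-randomised grouping assigns it to placebo. The control arm then consists partly of patients on the test drug, and the HR moves toward 1.

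Cohort B PFS is the key secondary endpoint. Because no alpha is spent on it, the estimated HR is its main output, so bias in that estimate is what matters. The timing of the rule matters too. SAP 6.13 requires no DMC for the Cohort B interim, so a rule chosen after that analysis would be chosen with Cohort B results in view.

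**Working it through.** **Inputs from the documents.** Cohort B size and allocation: "Approximately 150 patients will be randomized in a 2:1 ratio to Arm B1", that is 100 against 50 (SAP 5.2). Final analysis at about 105 events, or 1 − 105/150 = 30% censored (SAP 6.7.2.1). Design property: "80% of chance to observe a hazard ratio less than 0.824, assuming a true hazard ratio of 0.703 by study assumption" (SAP 5.2). SAP 5.2 does not give the event count behind the 80%; I take 105.

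**The plan's own figure.**
- Half of the effect size: 1/0.703 − 1 = 0.4225; half is 0.2112; 1/1.2112 = 0.826, against the stated 0.824. These agree apart from rounding.
- Probability by the Schoenfeld variance: Φ[(ln 0.824 − ln 0.703) × √(105 × 2/9)] = Φ[0.1588 × 4.830] = Φ(0.767) = 77.9%.
- With the event split expected under HR 0.703 (65.8 and 39.2): SE = √(1/65.8 + 1/39.2) = 0.202, giving 78.4%.
- Simulated Cox model without crossover (4,000 trials): average HR 0.70, probability 79.2%.

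The stated figure of roughly 80% is reproduced.

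**Effect of crossover.** Simulation of 100 against 50 patients, true HR 0.703, cut-off at the 105th event. When event number k occurs, every event-free placebo patient switches and her hazard is multiplied by 0.703 (full effect) or 0.85 (weaker effect) from then on. Assumptions not in the documents: exponential PFS, 12-month uniform accrual, control median 9 months, all switches at the same moment. There were 2,000 trials per cell, so the simulation error of a probability is at most √(0.25/2000) = 1.1 points. Average HR is the exponential of the mean log HR. P is the chance of an observed HR below 0.824.

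| k at switch | placebo switched, of 50 | as written: HR, P | censored at crossover: HR, P | as written, weaker effect: HR, P |
|---|---|---|---|---|
| 40 | 34.1 | 0.870, 41% | 0.700, 72% | 0.775, 62% |
| 50 | 30.2 | 0.842, 46% | 0.693, 73% | 0.762, 64% |
| 60 | 26.5 | 0.811, 52% | 0.698, 73% | 0.746, 68% |
| 70 | 22.8 | 0.782, 60% | 0.698, 75% | 0.737, 71% |
| 80 | 19.2 | 0.754, 67% | 0.693, 78% | 0.729, 71% |
| 90 | 15.8 | 0.732, 72% | 0.705, 77% | 0.713, 76% |

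Control medians of 5 and 14 months give nearly the same values. Over all three medians the as-written P runs from 39% to 72% and the censored P from 69% to 78%.

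**Price of a cut-off at crossover.** The same Schoenfeld formula with only the k events then available gives, for k = 40, Φ(0.1588 × √8.889) = Φ(0.473) = 68%, and for k = 90, Φ(0.1588 × √20) = Φ(0.710) = 76%. Against 77.9% at 105 events, the loss from fewer events is smaller than the loss from dilution under full effect.

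**The case against.** Several stronger readings are tempting, and the documents do not support them.

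- *That the 105-event HR is diluted by design.* It is not. That analysis is triggered by Cohort A stopping early, not by Cohort B crossing over, and it is worded as something that may be done. Protocol 8.1.1 describes this case as one in which Cohort B carries on. If only Cohort A crosses over, Cohort B is untouched. Dilution needs both a Cohort B crossover and a later Cohort B cut-off.
- *That 0.824 is a success criterion.* It appears only as a sample-size property of an endpoint tested descriptively, so no decision rule fails.
- *That the primary result is at risk.* Crossover can follow only a positive Cohort A interim, which is tested on data from before any switch. Only later Cohort A PFS updates could be affected.
- *That OS should be censored at crossover too.* SAP 6.7.2.2 says: "The final analysis of OS will be conducted together with the analysis of PFS at study completion", so OS would include time after a switch. But the patients who switch are the progression-free ones, and censoring them removes the placebo patients with the best prognosis. In simulations with no drug effect at all, as-randomised OS averaged HR 0.99 to 1.01, while OS censored at crossover averaged 0.66 to 0.91, a spurious benefit. (Assumed: 12-month accrual, median PFS 6 to 12 months, median post-progression survival 12 to 20 months, crossover at month 16 or 20, cut-off at month 36.)

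Two further objections stand in part. Sensitivity Analysis 1 could cover the switch, and SAP 6.7.3 introduces its sensitivity analyses as serving both the primary and the key secondary analysis. But its wording leaves crossover unclear, and it would not change the main analysis. Full, simultaneous crossover with an immediate full effect is also close to a worst case, which is why the weaker-effect column is shown. Partial crossover would dilute less.

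**Conclusion.** The gap is real but conditional. If Cohort B placebo patients switch before progression and before the Cohort B final cut-off, the written rules give an HR biased toward 1. With full crossover after 40 to 90 of 105 events the average HR is about 0.73 to 0.87 instead of about 0.70, and the chance of an HR below 0.824 is about 39% to 72% instead of about 79%. With a post-switch hazard multiplier of 0.85 the figures are 0.71 to 0.78 and 62% to 76%. The effect is nil if Cohort B does not cross over or if its 105 events are already in.

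These sizes rest on the assumed timing, completeness and effect of the switch, and on switching before progression, which is inferred from the rule that study drug stops at progression. The point concerns the estimate for a descriptive key secondary endpoint. It does not touch the type I error or the Cohort A interim test.

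**What to change.** 1. Add to SAP Table JPBQ.6.1 and protocol Table JPBQ.12.1: if a cohort crosses over, its main PFS analysis uses data up to the crossover date. This can be a data cut-off at crossover, or censoring at the last adequate tumour assessment before the first crossover dose. The cut-off is the cleaner choice, because censoring switchers may be informative when patients choose whether to switch.
2. Report the as-randomised PFS result over full follow-up alongside.
3. State in SAP 6.7.3 that Sensitivity Analysis 1 counts crossover to abemaciclib as a new therapy.
4. Reconcile two statements in the same paragraph of SAP 6.13 (and protocol 12.2.14): that all patients stay blinded and in PFS follow-up until study completion, and that the sponsor may stop a cohort early, unblind it and allow crossover.
5. Do not add an OS analysis censored at crossover.

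The cost is a few sentences and one additional presentation of PFS. The drawback is that the main Cohort B analysis may then have fewer than 105 events. The SAP should say so and state that the analysis proceeds with the events available. The rule should be fixed before any unblinded Cohort B result is seen.

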## 6.14. Annual Report Analyses

Annual report analyses, including Developmental Safety Update Report (DSUR) and Investigational Brochure (IB) analyses, are described in the abemaciclib Program Safety Analysis Plan.

## 6.15. Clinical Trial Registry Analyses

Additional analyses will be performed for the purpose of fulfilling the Clinical Trial Registry (CTR) requirements.

Analyses provided for the CTR requirements include the following:

Summary of adverse events, provided as a dataset which will be converted to an XML file. Both Serious Adverse Events and ‘Other’ Adverse Events are summarized: by treatment group, by MedDRA preferred term.

- An adverse event is considered ‘Serious’ whether or not it is a treatment emergent adverse event (TEAE).
- An adverse event is considered in the ‘Other’ category if it is both a TEAE and is not serious. For each Serious AE and ‘Other’ AE, for each term and treatment group, the following are provided:
  - the number of participants at risk of an event
  - the number of participants who experienced each event term
  - the number of events experienced.
- Consistent with [www.ClinicalTrials.gov](http://www.ClinicalTrials.gov) requirements, ‘Other’ AEs that occur in fewer than 5% of patients/subjects in every treatment group may not be included if a 5% threshold is chosen (5% is the minimum threshold).
- AE reporting is consistent with other document disclosures for example, the CSR, manuscripts, and so forth.

In addition, a participant flow will be created that will describe how many enrolled patients completed the study, and for those who did not, the frequency of each reason for not completing. This analysis will be based on study discontinuation, not treatment discontinuation. A patient will be identified as having completed the study if the patient dies while on the study or the patient had discontinued study treatment and is in follow up at the time of the final analysis. Patients who withdraw consent before the final analysis or who are still on treatment at the time of the final analysis will be identified as not completing the study.

## 7. Unblinding Plan

Randomization will occur using an IWRS system. Assignment to treatment groups within a cohort will be determined by a computer-generated random sequence. Security measures will be taken so that treatment group code that can link patients to study arm will be blinded in the database.

In order to maintain the scientific integrity of this double-blind trial, access to study data will be strictly controlled prior to the interim and final analyses. Dummy treatment assignment will be used in the reporting database until the database lock for the final analysis. During this time, analyses using unblinded treatment codes will be performed only at the interim analysis points specified in the protocol/SAP. For those safety and efficacy analyses assigned to the DMC, only the designed Statistical Analysis Center (SAC), who is independent of the sponsor, will perform analyses on unblinded data.

Data sets will be created for the purpose of aggregate data review by the sponsor in which treatment assignment is scrambled so that personnel involved in the day-to-day conduct of the trial and development and validation of analysis programs will be blinded to patient treatment assignment.

While every effort will be made to blind both the patient and the investigator to the identity of the treatment, the inadvertent unblinding of a patient may occur. This unblinding will not be sufficient cause (in and of itself) for that patient to be excluded from any safety or efficacy analyses.

